### **2.5. Secondary Outcome**

Secondary outcomes include:

1. Completion rate of both first and second trimester scans (when considered as a single instrument to visualize the fetal anatomy, what is the rate of complete visualization divided by all women?)
2. Total length of scanning time in the first trimester ultrasound group
3. Number of anomalies identified (and missed) in each group
4. Neonatal outcomes (survival, gestational age at delivery, NICU admission, hospital LOS, neonatal morbidities including respiratory distress syndrome, transient tachypnea of the newborn, intraventricular haemorrhage, necrotizing enterocolitis)
5. Patient feedback to standardized surveys (see attached)

6. Cost of intervention compared to usual care (cost benefit analysis based on whether more ultrasounds were done in cases of early discovery of anomalies)

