trimester ultrasound by the clinical team as part of standard obstetrical care and completes a survey regarding her satisfaction with this technique via email. Research staff will ensure patients have this scan scheduled and completed, as it is part of study procedure. Data about this scan will be recorded in the patient's research record. This scan can be repeated as indicated according to UT's protocol for assessing anatomy.

*c. Final Study Visit:*

The final study visit is denoted by completion of the second trimester gold standard scan (GSS) for patients randomized to the intervention arm, and at the completion of the second trimester anatomy ultrasound for patients randomized to the comparison arm. Participants will continue to be followed through their pregnancy to document the number of ultrasounds required to complete the fetal anatomy evaluation.

*d. Post Study Follow up and Procedures*

Medical records will be reviewed after each study participant's due date to assess whether delivery has occurred and to record delivery outcomes from the medical records, when available. This is chiefly so that a post-natal evaluation can be recorded to confirm or exclude anatomical anomalies. Delivery outcomes are not a primary outcome and request of outside delivery records will not be required for a subject's record to be marked as completely collected.

Adverse outcomes, including discomfort during ultrasound as well as neonatal outcomes, will be recorded in the subject's research record.

*e. Discontinuation Visit and Procedures*

Subjects may withdraw voluntarily from participation in the study at any time. Subjects may also withdraw voluntarily from receiving the study intervention for any reason.

If a patient in the intervention arm withdraws from the study during to her first trimester anatomy ultrasound, she will be asked to complete the survey regarding her experience regardless of the duration of the first trimester ultrasound. She will then undergo her clinically indicated ultrasound (which are not transvaginal).

If a subject in the intervention arm withdraws from the study prior to her second trimester GSS ultrasound (done as "back up" for the intervention), a standard email will be sent to her confirming her withdrawal and encouraging her to seek a second trimester (standard of care) anatomy ultrasound as the anatomy evaluation she had in the first trimester is considered experimental.

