## **7.2. Safety Monitoring Plan**

The research ultrasound will be stored locally on an E8 machine or on a hard drive owned and protected by UT. It will not be available in the medical record. Data regarding ultrasound (length in minutes, date, gestational age, findings) will be stored in RedCap. Maternal and neonatal outcomes will be collected from Care4 or Epic (depending on the location of delivery) and stored in RedCap.

Adverse effects are not expected from an ultrasound intervention, although discomfort especially with transvaginal ultrasound is frequently reported by patients. In the case of patient discomfort with the ultrasound exam, the exam will be paused and the patient asked for permission to continue. If the patient declines the continuation of the exam, the exam will stop and completion will be assessed based on the images obtained before that point.

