## **9.2. Statistical and Analytical Plans**

Analysis will be carried out according to the intention-to-treat principle. All randomized subjects will be included in analyses for which they have data. Frequentist statistics will be reported, including mean number of scans in each group (compared with t tests, with ANOVA between classes of obesity), the proportion of complete scans in each group (compared with chi square test), and the mean total scan time (t tests). Secondary outcomes will also be analysed with a frequentist approach. Descriptive statistics will also be provided about anomalies found and missed (anticipated to be low, so likely few significant findings to report). In addition, patient perspectives will be described.

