**Withdrawal Email 1 (for intervention arm, withdrawing during her detailed first trimester ultrasound)**

Dear [Name],

We are sorry to see you go! Thank you for considering EASE-O, a randomized clinical trial to find out when is the best time for a detailed anatomy ultrasound in women with a BMI of 35 or greater. This email confirms that you have withdrawn from the study. Your data will not be analyzed and no further data will be collected.

You do not have to do anything further, but we ask that you tell us about your experience during your ultrasound, at [this link](#). Filling out this survey helps us understand what women like you prefer regarding their ultrasounds. We want to hear from you!

Sincerely,

[name]  
Principle Investigator, EASE-O

**Withdrawal Email 2 (for intervention arm, withdrawing after her detailed first trimester ultrasound, before her safety second trimester ultrasound)**

Dear [Name],

We are sorry to see you go! Thank you for participating in EASE-O, a randomized clinical trial to find out when is the best time for a detailed anatomy ultrasound in women

with a BMI of 35 or greater. This email confirms that you have withdrawn from the study. Your data will not be analyzed and no further data will be collected.

You do not have to do anything further, but we encourage you to seek out an ultrasound between 18 and 22 weeks gestational age, if you haven't already gotten one. You did have an ultrasound in the first trimester looking at all the baby's parts, but these ultrasounds are still considered experimental (that's why we are researching them)! You deserve a later ultrasound, it is still recommended and will be covered by your insurance as part of your routine prenatal care.

Sincerely,

[name]  
Principle Investigator, EASE-O

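### The protocol asks women who withdraw during the first trimester scan for a survey, while the withdrawal email tells them their data will not be analysed; sections 4.3.e and 9.2 and the withdrawal emails must be reconciled

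*Combined protocol and SAP*

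**What the plan says.** Patient feedback from the standardized survey is secondary outcome 5 in section 2.5. The survey in Appendix 1 asks about satisfaction, discomfort, scan length and whether the woman would choose the same timing again.

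Three places deal with data from a woman who withdraws during the first trimester scan:

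- **Section 4.3.e** (Discontinuation Visit and Procedures): "she will be asked to complete the survey regarding her experience regardless of the duration of the first trimester ultrasound".
- **Withdrawal Email 1** (Standardized Emails), addressed to intervention-arm women who withdraw during that scan: "Your data will not be analyzed and no further data will be collected". Its next paragraph begins "You do not have to do anything further, but we ask that you tell us about your experience during your ultrasound" and gives the survey link.
- **Section 9.2**: analysis is by intention to treat, and "All randomized subjects will be included in analyses for which they have data".

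Email 2 (withdrawal after the first trimester scan and before the second) and Email 3 (comparison arm, before the second trimester scan) carry the same statement that data will not be analysed. Section 3.6 replaces women who withdraw.

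Discomfort is also captured outside the survey. Section 4.3.d says "Adverse outcomes, including discomfort during ultrasound as well as neonatal outcomes, will be recorded in the subject's research record", and section 7.1 has it noted in the study database. Section 7.2 acknowledges that "discomfort especially with transvaginal ultrasound is frequently reported by patients".

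**The concern.** Section 4.3.e sets out to hear from women who leave mid-scan, however short the scan was. The email to those women promises that nothing they have given will be used and nothing more will be gathered, and then asks them for more. Section 9.2 would analyse whatever exists. The text does not say which of these prevails.

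The site therefore has two poor options. If it honours the email, it discards replies that section 4.3.e exists to obtain and departs from section 9.2. The discarded replies are plausibly the least favourable, so their absence would be informative. Replacement under section 3.6 would restore the head count and make the gap harder to see. If the site follows section 9.2, it analyses data after telling the participant in writing that it would not. A named secondary outcome and a statement made to participants are at stake. The primary outcome is not part of this point.

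**Working it through.** No figure in the plan bears on this point, so there is none to reproduce. The main check is to compare the rules for each kind of woman.

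| Situation | Survey requested? | Data analysed? |
|---|---|---|
| Stops the first trimester scan for discomfort, stays in the study | Yes (4.3.b) | Yes: completion is judged on the images obtained (7.2), and nothing removes her survey |
| Withdraws from the study during that scan | Yes (4.3.e and Email 1) | No (Email 1); yes (9.2) |
| Withdraws after that scan, before the second trimester scan | Already requested after the scan (4.3.b) | No (Email 2); yes for data held (9.2) |
| Comparison arm, withdraws before the second trimester scan | Not required (4.3.e) | No (Email 3); yes for data held (9.2) |

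The second row contains the direct contradiction. Rows three and four show that the conflict with section 9.2 extends to all three emails. Section 3.4 adds a further route: it excludes from analysis women who did not receive a second trimester ultrasound, and it does not say whether that covers the survey.

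**Illustration of size.** Inputs:

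- 59 women in the intervention arm (section 4.1: 19 + 20 + 20).
- Assumption: 10 of the 59 would rate the scan uncomfortable.
- Assumption: k of those 10 withdraw mid-scan and their replies are dropped.
- Assumption: every other woman replies.

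Reported share = (10 − k)/(59 − k).

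- k = 0: 10/59 = 16.9%
- k = 1: 9/58 = 15.5%
- k = 3: 7/56 = 12.5%
- k = 5: 5/54 = 9.3%

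If replacements resemble the women who stayed, replacement brings the denominator back to 59 but leaves the expected share unchanged.

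A second parameterisation avoids fixing the 10. Let w women withdraw, all of them uncomfortable, and let q be the uncomfortable share among the rest. The true share is (q(59 − w) + w)/59. Dropping the w women reports q, so the understatement is w(1 − q)/59. For q from 30% down to 10%:

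- w = 1: 0.7/59 to 0.9/59, or 1.2 to 1.5 percentage points
- w = 3: 2.1/59 to 2.7/59, or 3.6 to 4.6 points
- w = 6: 4.2/59 to 5.4/59, or 7.1 to 9.2 points

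The result depends chiefly on w, which the documents do not give. With w = 0 there is no bias.

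**The case against.** The strongest reply is that this is a wording slip with little statistical consequence. Much of that reply stands.

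- A reader might infer that every woman who stops the scan is lost, so that the survey would describe only women who tolerated it. Section 7.2 does not support this: a woman who declines to continue is not thereby withdrawn. Section 4.3.e also separates leaving the study from declining the intervention. Only women who withdraw from the study are affected.
- A reader might infer that the discomfort data disappear. They are also recorded outside the survey (sections 4.3.d and 7.1), and are lost only if the email's statement is applied to that record too, which the documents leave open. Satisfaction and timing preference have no stated second source.
- A reader might infer a large bias, for example half of the discomfort signal. That figure is simply the assumed case of 5 withdrawals among 10 uncomfortable women. Numbers may well be small, since enrolment requires agreement to a transvaginal scan if needed (section 3.3) and women can stop without withdrawing.
- A reader might infer that the loss is certain and falls only on the intervention arm. Section 9.2 would keep replies already held. Withdrawal during the second trimester scan has no stated procedure, so a like-for-like comparison of the arms is not possible.
- Email 1 already leaves the survey optional, and section 9.2 plans only a description of patient perspectives.

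None of this removes the contradiction. Optional completion does not settle whether a returned survey may be used, and a descriptive summary is still distorted if its least favourable replies are omitted.

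**Conclusion.** The point holds as an inconsistency between stated rules. Section 4.3.e, section 9.2 and the withdrawal emails cannot all be followed for a woman who withdraws during the first trimester scan, and the emails conflict with section 9.2 for other withdrawals too. If the emails prevail, secondary outcome 5 plausibly loses some of its least favourable intervention-arm replies. If section 9.2 prevails, a written assurance is broken.

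The direction of bias rests on the assumption that women who leave mid-scan found it less acceptable than those who stayed. Its size cannot be estimated from the documents; the range of 15.5% to 9.3% against 16.9% is an illustration under assumed inputs. This should be corrected, but it does not bear on the primary comparison.

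**What to change.** 1. Reconcile section 4.3.e, section 9.2 and Withdrawal Emails 1, 2 and 3 on one rule for data gathered before withdrawal and for a survey returned afterwards. The rule must agree with the consent terms, which are not in the text available here.
2. If consent allows, reword the emails to say that data collected up to withdrawal, and any survey the woman chooses to return, will be analysed. Do not justify this as safety reporting, because section 7.1 says discomfort is not passed to a safety monitor.
3. In section 9.2, report survey replies and recorded discomfort for all women who started their detailed scan, including those who withdrew during it. Give the number stopping or withdrawing mid-scan by arm and reason. State that the section 3.4 exclusion for a missing second trimester scan does not remove these replies.
4. If consent does not allow use of these data, remove the survey request from section 4.3.e and Email 1. Report the number who withdrew mid-scan, if consent permits, as a limitation of secondary outcome 5.

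The cost is a small change to three emails and section 9.2, plus one row in a results table. Patient-reported results for the first trimester scan may look slightly less favourable.

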## 5. TRIAL MATERIALS

### 5.1. Ultrasound Systems

All scans (screening ultrasound, first-trimester anatomy scan, GSS, and second trimester anatomy scans) will be performed using General Electric (GE) E8 or E10 machines, which are FDA approved for ultrasound in the first and second trimester (E8 510(k) number: K170445, E10 510(k) number: K173555). Approval for the E8 is available at [https://www.accessdata.fda.gov/cdrh\\_docs/pdf17/K170445.pdf](https://www.accessdata.fda.gov/cdrh_docs/pdf17/K170445.pdf) (last accessed 7/30/20) and approval for the E10 is available at [https://www.accessdata.fda.gov/cdrh\\_docs/pdf17/K173555.pdf](https://www.accessdata.fda.gov/cdrh_docs/pdf17/K173555.pdf) (last accessed 7/30/20).

## 6. BLINDING

Patients are not blinded to their group as they are aware of the timing of their detailed ultrasound. The clinical team will not be informed of the patient's randomization assignment, images from research ultrasounds will not be available to the clinical team, and the clinical team will not be made aware of whether the second trimester scan done by them is for comparison to the gold standard (the GSS in intervention arm patients) or for anatomy (in comparison arm patients).

Patients and the care team will be unblended from the results of the first trimester exam if there is an anomaly. There are no other plans for unblinding.

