##### *b. Study Visits and Procedures*

After the screening ultrasound confirms eligibility and a patient is given informed consent, the patient can then be randomized. If the patient is randomized to the intervention (detailed first trimester anatomy ultrasound), this scan is performed at the randomization visit if the patient is between 12w0d and 13w6d. If she is less than 12w0d, a separate study visit is scheduled for a date at her convenience during the days she is between 12w0d and 13w6d. A dedicated room and time slots have been made available for these study visits at Memorial Hermann Southwest and at the Fetal Center at UTPB. This separate scan/visit is not billed as it is not part of the standard of care.

After this detailed research ultrasound, which will be limited to 15 minutes, she then receives her clinically indicated dating ultrasound or nuchal translucency measurement. The total estimated time of all these ultrasounds is expected to be approximately 30 minutes, with breaks in between to allow the patient some movement and the opportunity to use the rest room, and to allow the exchange of operators (research staff vs clinical staff) and the creation of distinct records (research ultrasound is not saved to electronic medical records, so a new scanning encounter must be opened for the clinical ultrasound that day). The patient will complete a survey about her satisfaction with this technique via email. In addition, as a safety measure, if an anomaly is suspected on the day of the detailed first trimester anatomy scan, the patient will be unblinded. The research team will inform the clinical team so that a more detailed evaluation can be done and so that this information can enter the clinical record and affect clinical management.

Patients randomized to the intervention arm are later scheduled for a second trimester ultrasound by the clinical team, as this is part of standard obstetrical care. Research staff will ensure patients have this scan scheduled and completed, as it is part of study procedure. Data about this scan will be recorded in the patient's research record. This scan can be repeated as indicated according to UT's protocol for assessing anatomy.

If the patient is randomized to the comparison arm, she does not undergo a detailed first trimester ultrasound that day, but she does receive her clinically indicated limited ultrasound for dating or for nuchal translucency. She then undergoes a second

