#### Standardized Welcome Email

Dear [Name],

Thank you for participating in EASE-O, a randomized clinical trial to find out when is the best time for a detailed anatomy ultrasound in women with a BMI of 35 or greater. We're so glad you're part of the study. If you haven't already filled out your demographics with the research staff, please click [this link](#) to do so.

You are in the group that gets a detailed anatomy ultrasound in the [first/second] trimester. Based on this, a survey [has been/will be] made available to you about your experience after your detailed anatomy ultrasound. Filling out this survey helps us understand what women like you prefer regarding their ultrasounds. We want to hear from you!

Because you are in the group that gets a detailed anatomy ultrasound in the [first/second] trimester, your next step in the study is to get [an ultrasound to check on the baby/your detailed anatomy ultrasound] between 18 and 22 weeks, which will be scheduled by your doctor. You don't have to do anything—we'll take care of everything, and all your information will be kept confidential.

If you have any concerns about the study or want to withdraw, please email [[contact]](mailto:[contact]). Have a great day!

Sincerely,

[name]  
Principle Investigator, EASE-O

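### Section 6 promises that the clinical team stays unaware of allocation at the second trimester scan, but the visit order, the participant emails and the scan-time estimates leave that promise unprotected.

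*Combined protocol and SAP*

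**What the plan says.** Section 6 sets out the masking. Participants are open: "Patients are not blinded to their group as they are aware of the timing of their detailed ultrasound". For the clinical side it promises "The clinical team will not be informed of the patient's randomization assignment, images from research ultrasounds will not be available to the clinical team". It makes a second promise about the later scan: "the clinical team will not be made aware of whether the second trimester scan done by them is for comparison to the gold standard". The gold standard scan (GSS) is the back-up second trimester scan in the intervention arm. The only exception is a suspected anomaly on the first trimester research scan, which is disclosed.

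Section 4.3.b gives the visit order. For an intervention woman, "this scan is performed at the randomization visit if the patient is between 12w0d and 13w6d"; if she is under 12w0d she returns for a separate research visit. The order on the day is: "After this detailed research ultrasound, which will be limited to 15 minutes, she then receives her clinically indicated dating ultrasound or nuchal translucency measurement". Scanning time is planned "with breaks in between to allow the patient some movement"; another stated reason for the pauses is "to allow the exchange of operators (research staff vs clinical staff) and the creation of distinct records". A comparison woman has only the limited clinical scan that day, after the eligibility scan common to both arms. The clinical team does the second trimester scan in both arms.

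The welcome email in Appendix 3 tells each woman: "You are in the group that gets a detailed anatomy ultrasound in the [first/second] trimester". Two further emails, one per arm and sent around the second trimester scan, name the group again. Section 7.1 lists estimated scan times: 45 minutes for the GSS and 30 for the comparison arm's second trimester scan.

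**The concern.** Clinical-team masking is the only masking the plan describes. The research operator of the first trimester scan necessarily knows the arm, the women know it, and no masked independent reader of completeness is mentioned.

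That masking covers the comparator of the primary outcome. Under section 2.4 a scan counts as complete only if every listed view is seen, so persistence over one last view can decide the result. The comparison arm's second trimester scan is one side of the chi-square test in section 9.2. The GSS feeds the combined completion rate and the count of missed anomalies in section 2.5. A sonographer who knows that a woman has already had a detailed early look may try less hard, or harder, for a difficult view.

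A promise not to tell the clinical team does not by itself keep the team unaware. The question is whether any procedure in the plan does so.

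**Working it through.** This is mainly a comparison of sections, with two small calculations.

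1. **What first trimester clinical staff can observe on a same-day visit.**
   - Intervention arm: eligibility scan, detailed research scan (capped at 15 minutes in section 4.3.b, estimated at 25 in section 7.1), change of operators, clinical scan.
   - Comparison arm: eligibility scan, clinical scan.
   - The presence of research staff is not in itself revealing, because recruitment and the eligibility scan occur in both arms. The extra detailed scan and the delay are what differ, and they allow the arm to be inferred.

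2. **Whom this affects.** Only intervention women at 12w0d to 13w6d when randomised. The share is not given.

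3. **Distance from the masked scan.** The windows are 12w0d to 13w6d and 18w0d to 22w6d.
   - Shortest gap: 18w0d − 13w6d = 126 − 97 = 29 days.
   - Longest gap: 22w6d − 12w0d = 160 − 84 = 76 days.
   - What is learned at the first visit therefore reaches the second trimester scan only if the same person scans again and remembers, or passes it on. The documents neither say that this happens nor describe anything that prevents it.

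4. **The participant's route.** This one can act at the second trimester scan itself. Women are unmasked. The welcome email names the group. The intervention-arm reminder names it again and says the later scan is approaching. The comparison-arm email names it and may arrive before or after the scan. None asks the woman not to mention her group to the sonographer.

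5. **Scan-time estimates.** GSS 45 minutes, comparison scan 30 minutes: a planned difference of 45 − 30 = 15 minutes, or 45/30 = 1.5 times as long. Section 1.2.d says both are judged against the same second trimester image protocol, and section 6 says the operators do not know which one they are doing. No reason for the difference is given.

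6. **Scale only.** Section 4.1 plans 19 + 20 + 20 = 59 women per arm. One scan changing between complete and incomplete moves an arm's rate by 1/59 = 1.7 percentage points. The 15-point difference sought in section 9.1 corresponds to 0.15 × 59 = 8.85, about 9 scans. This shows how sensitive the outcome is to a few scans. It does not estimate how many would change.

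**The case against.** A reader might infer that the visit order defeats the masking of the second trimester scan, with clinical staff taking over straight from the research operator. The documents do not support that.

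- The handover is at a different visit, 29 to 76 days before the scan in question.
- The documents speak of clinical staff at the first trimester change of operators and of the clinical team for second trimester scans. They never say that the same individuals do both, and recruitment spans several clinics.
- Breaks and a new scanning encounter come between the research and clinical scans. Research images stay out of the medical record (sections 4.3.b and 7.2), so a later operator has no chart trail.
- Women under 12w0d have their research scan at a separate visit.

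It can also be said that section 6 promises only that the study will not tell the team, and openly concedes that women know their group. A woman who mentions it contradicts nothing. The second trimester scans in both arms are standard care judged by one protocol, which limits the room for arm-dependent effort.

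All of this stands, and it rules out the stronger reading. Three gaps remain: same-day first trimester clinical staff can infer the arm, no step keeps second trimester operators unaware, and the differing time estimates are unexplained. Disclosure for a suspected anomaly is planned and is not in question.

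**Conclusion.** The only masking described for the primary comparator rests on a statement of intent that the procedures do not protect. Allocation can be inferred by first trimester clinical staff in same-day intervention cases, and can be disclosed by any participant at the second trimester scan. The 45 and 30 minute estimates sit poorly with operators said to be unaware.

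The documents do not show that masking fails, and they give no basis for a size or direction of bias. Any assumed shift in completion would be a guess. The conclusion assumes only that a sonographer's knowledge of the arm could influence effort or scoring on an all-or-nothing outcome. The point merits action because the safeguards cost almost nothing, not because a bias has been demonstrated.

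**What to change.** 1. Add one sentence to the welcome email and to both second trimester emails asking women not to tell the second trimester sonographer which group they are in. The welcome email matters most for the comparison arm, whose later email may arrive after the scan.
2. At each second trimester scan, record whether the sonographer knew the arm, preferably once completeness has been scored. Report a sensitivity analysis of second trimester completion by awareness. Awareness is not randomised, so this is descriptive.
3. For same-day visits, where clinic flow allows, show the allocation to research staff only and do the clinical scan before the research scan. Keep the section 4.3.b route for telling the clinical team of a suspected anomaly. Staff may still notice a woman staying on, so this reduces the exposure but does not remove it.
4. Reconcile the 45 and 30 minute estimates in section 7.1 with section 6, and state whether second trimester operators and readers are different people from the first trimester clinical staff.

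The cost is one email sentence, one data field, some clinic-flow planning and a short text clarification. No extra scan is needed.
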